5.2 PARTICIPANT EXCLUSION CRITERIA

Any of the following is a criterion for exclusion from the study:

1. Any of the following laboratory abnormalities:
 - a. Platelets, $< 35 \times 10^9/L$
 - b. Absolute neutrophil count (ANC) $< 1.0 \times 10^9/L$ (independent of growth factor for 7 days)
 - c. Creatinine clearance $< 30 \text{ ml/min}$
 - d. Serum amylase and lipase $> 1.5 \times \text{ULN}$
 - e. Aspartate aminotransferase (AST) or alanine aminotransferase (ALT) $> 2.5 \times \text{ULN}$,
 - f. Total bilirubin $> 1.5 \times \text{ULN}$, Patients with a total bilirubin between $1.5 - 3.0 \times \text{ULN}$ are eligible if the direct bilirubin fraction is $< 25\%$ of the total bilirubin
2. Accelerated phase or blast phase disease as defined by peripheral or bone marrow blast percentage $> 10\%$
3. Patient is pregnant or lactating female
4. Patient is a woman of childbearing potential as previously defined in inclusion #7, unless using effective contraception while on study treatment
5. Patient is a man who is a partner with of a woman of childbearing potential, unless they agree to use effective contraception while on study treatment as previously defined in inclusion #9.
6. Patient with prior history of encephalopathy, including Wernicke's Encephalopathy (WE)
7. Patient has signs or symptoms of encephalopathy, including Wernicke's Encephalopathy (e.g. severe ataxia, ocular paralysis or cerebellar signs) in which case thiamine deficiency needs to be excluded and a brain MRI might be required to exclude possible Wernicke's encephalopathy
8. Patient has thiamine deficiency if not corrected before enrollment on the study
9. Patient with concomitant treatment with or use of pharmaceutical or herbal agents known to be moderate or strong inducers of CYP3A4 or dual CYP3A4 and CYP2C19 inhibitors. For a list of moderate or strong inhibitors or inducers of CYP3A4, see table 3-2 and 3-3 at <https://www.fda.gov/drugs/drug-interactions-labeling/drug-development-and-drug-interactions-table-substrates-inhibitors-and-inducers>.
10. Patient on any chemotherapy, immunomodulatory drug therapy (e.g., lenalidomide, pomalidomide, thalidomide, interferon-alpha), ruxolitinib, anagrelide, corticosteroids $> 10 \text{ mg/day}$ prednisone or equivalent. Patients may remain on hydroxyurea (e.g., hydrea) if it is being employed to control leukocytosis as long as the patient has been on a stable dose for > 14 days prior to initiation of fedratinib.
11. Prior treatment with fedratinib
12. Patient on treatment with myeloid growth (e.g. G-CSF) factor within 14 days prior to initiation of fedratinib
13. Patient on treatment with aspirin with doses $> 150 \text{ mg daily}$.
14. Patient with diagnosis of chronic liver disease (e.g., chronic alcoholic liver disease, autoimmune hepatitis, sclerosing cholangitis, primary biliary cirrhosis).
15. Patients with active (uncontrolled, metastatic) second malignancies are excluded.
16. Patient with uncontrolled congestive heart failure (New York Heart Association Classification 3 or 4).
17. Patient with known human immunodeficiency virus (HIV), active infectious Hepatitis B (Hep B), and/or active Hepatitis C (Hep C).

- a. Patients with known HIV are eligible if the following criteria are met:
 - i. Patient has CD4+ T-cell count \geq 350 cells/ μ L
 - ii. Patient is on established anti-retroviral therapy (ART) (with medications that are not specifically excluded due to potential interactions within this study) for at least four weeks prior to study enrollment and have an HIV viral load less than 400 copies/mL prior to enrollment.
 - b. Patients with a history of Hep C infection are eligible if:
 - i. Pt has completed curative antiviral treatment and has hepatitis C viral load below the limit of quantification
 - ii. Pt has Hep C antibody positive but Hep C RNA negative due to prior treatment or natural resolution.
18. Patient with serious active infection requiring IV anti-microbials.
19. Patient with presence of any significant gastric or other disorder that would inhibit absorption of oral medication.
20. Patient is unable to swallow capsules.
21. Patient with participation in any study of an investigational agent (drug, biologic, device) within 30 days prior to start of fedratinib.
22. Patient has any condition including the presence of laboratory abnormalities, which places the patient at unacceptable risk if he/she were to participate in the study.
23. Patient has any condition that confounds the ability to interpret data from the study.
24. Any major surgery or radiation therapy within four weeks.

5.3 STRATEGIES FOR RECRUITMENT AND RETENTION

Recruitment of the 25 participants for this trial will occur from new or established patients treated at one of the participating sites. Screen failure is anticipated to be less than 10%. The target accrual is expected to be reached in 12-18 months. All faculty members in the myeloid sections of participating sites will be trained on the trial design, study agents, and eligibility criteria and will be offered the opportunity to be sub-investigators. This will equip each investigator to discuss the trial with potential participants as appropriate. The trial will be listed on the websites of the participating centers for the availability of local physicians to refer patients who could be eligible for the trial.

All investigators will be made aware of the emphasis to enroll women and minorities. The design of the trial and eligibility criteria are not restrictive relative to women and minorities.

Potential participants will be assessed prior to screening for any perceived barriers related to the clinical trial process. Referrals will be made to a social worker, supportive care services, financial services, or the research nurse to address barriers prior to consent.

5.4 PARTICIPANT WITHDRAWAL OR TERMINATION

5.4.1 REASONS FOR WITHDRAWAL OR TERMINATION

Patients may withdraw consent at any time for any reason or be dropped from the trial at the discretion of the investigator should any untoward effect occur that may jeopardize participant safety. In addition, a patient may be withdrawn by the investigator if enrollment into the trial is inappropriate, the trial plan is violated, or for administrative and/or other safety reasons.

A patient must be discontinued from the trial for any of the following reasons:

- The patient or legal representative (such as a parent or legal guardian) withdraws consent
- Unacceptable adverse events
- Dose delay lasting > 12 consecutive weeks
- Intercurrent illness that prevents further administration of treatment
- Investigator's decision to withdraw the patient
- The patient has a confirmed positive serum pregnancy test
- Noncompliance with trial treatment or procedure requirements
- The patient is lost to follow-up
- Administrative reasons
- Disease progression by proposed IWG response criteria for MDS/MPN¹ (Appendix H)
- Lack of response (including clinical benefit, marrow response, partial remission, complete remission) at week 24 assessment as defined by proposed IWG response criteria for MDS/MPN¹
 - a. In cases where the investigator believes a patient is clinically deriving a benefit from fedratinib despite not meeting pre-specified criteria for clinical benefit, continuation of fedratinib will need to be approved by the study PI.
- Requiring a medication/procedure on the prohibited medication/procedure list (refer to section 7.6)
- ≥ 3 dose reductions due to AE suspected to be related to study drug

The End of Treatment and Follow-up visit procedures are listed in the Schedule of Events and Section 7.3 (Visit Requirements). After the end of treatment, each patient will be followed for 30 days for adverse event monitoring. Patients who discontinue for reasons other than progressive disease will have post-treatment follow-up for disease status and toxicity up to 30 days. Follow-up rules will apply unless participant initiates a non-study cancer treatment, withdraws consent, or becomes lost to follow-up (unsuccessful attempts to contact for 3 months). After documented disease progression, each patient will be followed 104 weeks for overall survival until death, withdrawal of consent, or the end of the study, whichever occurs first.

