10.4.11 EXPLORATORY ANALYSES

- Overall Survival: OS will be measured for each patient on the study. OS will be defined as time from first treatment to death due to any cause or censored at last follow-up. OS will be measured by Kaplan-Meier method. Median OS, as well as OS rate at 1-year and 2-year will be reported

descriptively. The confidence interval will be computed by log-log transformation.

- Progression free survival: Progression will be measured for each patient as defined by Modified MDS/MPN IWG Proposed Criteria for Disease Progression in adult MDS/MPNs (Appendix H). PFS will be defined as time from first treatment to progression or censored at last follow-up. PFS will be measured by Kaplan-Meier method. Median PFS, as well as PFS at 1-year and 2-year will be reported descriptively. The confidence interval will be computed by log-log transformation.
- Duration of response: Response duration will be measured for each responding patient. Response and progression will be defined by Modified MDS/MPN IWG Proposed Criteria.¹ Duration of response is defined as the amount of time from the date of initial response to the date of disease progression or death.
- Correlation between mutations detected from NGS at baseline and response will be assessed using contingency tables and Mantel-Haenszel test to calculate relative risk and p-values.
- Correlation between the number of mutations detected from NGS at baseline and response will be assessed using cut-points of 2 and 3 mutations with relative risk and p-values calculated using contingency tables and Mantel-Haenszel test.
- For correlative study, the primary endpoint is the response. The difference between vehicle and fedratinib will be examined by Mantel-Haenszel test. The difference in survival between arms will be evaluated by the log-rank test. In addition, the agreement between PDX mouse response and patients' response will be measured by Kappa index.

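### Survival follow-up starts only at documented progression, so the exploratory 1- and 2-year OS and PFS estimates face probably informative censoring, of uncertain direction for OS

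*Combined protocol and SAP*

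**What the plan says.** Section 10.4.11 sets the analysis: "OS will be measured for each patient on the study". OS runs from first treatment to death from any cause and is censored at last follow-up. Median OS and 1- and 2-year OS come from Kaplan-Meier and are reported descriptively. PFS has the same landmarks and the same censoring rule.

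Section 5.4.1 sets the follow-up that has to supply those data.

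- Survival: "After documented disease progression, each patient will be followed 104 weeks for overall survival". It ends sooner if the patient dies or withdraws consent, or when the study closes.
- Everyone else: "Patients who discontinue for reasons other than progressive disease will have post-treatment follow-up for disease status and toxicity up to 30 days".
- General limit: "Follow-up rules will apply unless participant initiates a non-study cancer treatment, withdraws consent, or becomes lost to follow-up".

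The same section lists the mandatory reasons for discontinuation. They include "Unacceptable adverse events" and "Lack of response (including clinical benefit, marrow response, partial remission, complete remission) at week 24 assessment". A week-24 non-responder whom the investigator believes is benefiting may stay on drug, but "continuation of fedratinib will need to be approved by the study PI".

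Three other places bear on the point. Section 5.4.2 commits to making every effort to keep contact with early withdrawals, and says that patients who stay at the lead center may be tracked. Section 7.3.5 leaves evaluations after early termination to the physician, apart from adverse events. The schedule of events (7.3.7) ends at the End of Treatment visit and shows no survival contact.

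**The concern.** The follow-up rule cannot deliver what the analysis section promises. OS is to be measured in all patients, but a patient who stops without documented progression has no planned survival contact beyond 30 days. Disease status also stops at 30 days, so a later progression would not be captured and could not start the 104-week survival follow-up.

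Kaplan-Meier is valid when patients who are censored have the same later risk as those who remain. Here the exit is triggered by non-response or toxicity, both plausibly prognostic. At stake are the landmark OS and PFS figures, in a disease group for which the protocol quotes survival of 1 to 3 years (4.2.3) and calls OS a standard criterion of benefit.

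**Working it through.** **1. The plan's own figures.** The documents give no sample size, event count or precision for OS or PFS. The only design figures concern response (10.4.1): continue if at least 3 of 9 respond, reject if at least 12 of 25 respond, 30% versus 55%. With P(p) = Σ over x = 3..9 of C(9,x) p^x (1-p)^(9-x) × Pr[Bin(16,p) ≥ 12-x], P(0.30) = 0.0421 and P(0.55) = 0.8007. The stated 0.05 and 80% reproduce, and survival follow-up plays no part in them.

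**2. How many patients are exposed.** At the two design response rates, 25 × (1 - 0.55) = 11.25 and 25 × (1 - 0.30) = 17.5, so about 11 to 18 patients lack a primary-endpoint response. This is an upper bound. Some will already have died or progressed, marrow response counts as response for continuation in 5.4.1 but not for the primary endpoint, and some may continue with approval.

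**3. Bounds without a hazard model.** Assume 3 deaths before about week 28 (week 24 plus 30 days) and m patients censored there. One-year OS then lies between (25 - 3 - m)/25 and 22/25 = 88%, taking all other patients as alive at one year. For m = 5 the range is 68% to 88%. For m = 11 it is 44% to 88%.

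**4. Direction and size under assumed hazards.** The documents give only survival of 1 to 3 years, so every hazard below is an assumption. Each scenario simulated 200,000 patients with constant hazards. In the table, 45% are responders who stay on drug; the rest stop at week 24 (5.52 months). Toxicity stops occur at 0.01 per month. Under the 5.4.1 rule a patient is censored at discontinuation plus 30 days unless progression is documented by then. PFS counts progression or death. Medians are months of survival on drug / off drug without progression / after progression. Progression rates are per month, on / off drug. Cells show complete follow-up versus the 5.4.1 rule at 2 years.

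| Scenario | Medians | Progression | OS, % | OS error | PFS, % | PFS error |
|---|---|---|---|---|---|---|
| Off-drug patients worst | 36/8/12 | 0.03/0.06 | 33.7 vs 44.6 | +10.9 | 14.6 vs 28.3 | +13.7 |
| Off-drug as bad as progressors | 36/12/12 | 0.03/0.06 | 38.2 vs 45.3 | +7.1 | 17.1 vs 29.2 | +12.1 |
| Off-drug intermediate, progressors worst | 36/24/6 | 0.03/0.06 | 33.9 vs 35.3 | +1.4 | 20.8 vs 29.9 | +9.1 |
| Equal death hazards | 24/24/24 | 0.03/0.06 | 49.8 vs 49.7 | about 0 | 17.8 vs 23.4 | +5.6 |
| Off-drug like on-drug, progressors worst | 36/36/6 | 0.03/0.03 | 41.7 vs 36.4 | -5.3 | 30.7 vs 30.7 | 0 |
| As above, progression mainly on drug | 36/36/6 | 0.05/0.02 | 38.2 vs 27.5 | -10.7 | 27.8 vs 19.4 | -8.4 |

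Changing the responder share to 30% or 55% in the second row moves the OS error only to +7.4 or +6.6 points. Across all scenarios run, 39% to 52% of patients were lost alive under the rule and 26% to 50% of deaths before 24 months went unobserved.

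The OS sign varies because the rule drops non-progressors and keeps progressors, who may be the highest-risk group. PFS has no such counterweight, since progression is itself the event. Its sign follows whether progression is faster or slower off drug.

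**5. A separate limit.** With uniform accrual over 18 months and a 36-month study, 6/18 of 25, about 8 patients, cannot reach 24 months. That censoring is administrative and is not the problem described here.

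**The case against.** **A reader might infer that OS is overstated.** A two-group calculation supports that impression. Take medians of 36 months in responders and 12 in non-responders, a 30% response rate, and all surviving non-responders censored at 6.5 months. True 2-year OS is 0.30 × 0.63 + 0.70 × 0.25 = 36%. The estimate would be S(6.5) × S_resp(24)/S_resp(6.5) = 0.745 × 0.714 = 53%. At a 55% response rate the pair is 46% and 57%. The arithmetic is right, but it assumes a threefold survival gap that the documents do not give and that no non-responder ever has documented progression. If half do, the estimates fall to 41% and 50%, an excess of 4 to 5 points. The documents do not support a fixed upward direction for OS.

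**A reader might also infer that starting another cancer treatment ends survival follow-up.** That clause precedes the survival sentence, which lists its own end points. It is one reading, not a stated rule.

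**Section 5.4.2 mitigates the gap.** It does in part. But the commitment to keep contact has no survival item or schedule, and the tracking is optional and covers the lead center only, while four sites enroll.

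**OS and PFS are exploratory and descriptive, with no planned comparison.** This stands. So does the limit on precision: with 25 patients the standard error of a 36% survival rate is √(0.36 × 0.64/25), about 10 points, even with complete follow-up. These facts limit the weight of the point. They do not remove the conflict between 5.4.1 and 10.4.11.

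**Conclusion.** The conflict between the follow-up rule and the planned analysis is established from the text alone. That the censoring is informative is probable rather than proven; it rests on non-response and toxicity being related to later survival or progression. For OS the direction is unknown, with 2-year error of about -11 to +11 points under the assumed hazards and none if death hazards are equal. For PFS an upward error is more likely, at +6 to +15 points at 2 years where patients progress faster off drug (the top of that range comes from the 30% responder share); it is about zero with equal rates and negative with slower ones. At most 11 to 18 of 25 patients are affected. The primary endpoint, the futility rule, the sample size and the power are untouched, so this is an inexpensive improvement to exploratory results.

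**What to change.** Amend the follow-up paragraph of 5.4.1 so that all patients who receive at least one dose are followed for survival by periodic telephone or chart check, for example every 12 weeks, until death, withdrawal of consent or end of study, whatever the reason for stopping and regardless of later therapy. Take progression status from routine records over the same period. Bring 7.3.5 and the schedule of events into line, and state in 10.4.11 the censoring date for each endpoint. The same edit could settle whether death is a PFS event, which 10.4.11 does not say. No treatment or discontinuation rule needs to change.

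If survival and progression status are obtained for everyone as specified, this source of censoring disappears, and the estimates match the complete-follow-up values in every scenario above. The cost is an amendment and periodic contacts for at most about 18 more patients. The schedule of events shows no survival contact even for progressors, so the procedure has to be written down for all patients.

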5.4.2 HANDLING OF PARTICIPANT WITHDRAWALS OR TERMINATION

Every effort will be made to maintain contact with a patient who withdraws early. If the patient remains at MCC for further care, clinic visits may be tracked and the condition of the patient followed. If the patient is not continuing care at MCC, contact information will be updated at the end of treatment visit, including accurate phone numbers, and email address. The importance of the follow-up period for AEs and SAEs will be stressed to the patient.

Replacement of participants is permitted for those who fail to meet the eligibility requirements of the study.

5.5 PREMATURE TERMINATION OR SUSPENSION OF STUDY

This study may be temporarily suspended or prematurely terminated if there is sufficient reasonable cause. Written notification, documenting the reason for study suspension or termination, will be provided by the suspending or terminating party to investigator, funding agency, the IND/IDE sponsor and regulatory authorities. If the study is prematurely terminated or suspended, the PI will promptly inform the IRB and will provide the reason(s) for the termination or suspension.

Circumstances that may warrant termination or suspension include, but are not limited to:

1. Quality or quantity of data recording is inaccurate or incomplete
2. Poor adherence to protocol and regulatory requirements
3. Incidence or severity of adverse drug reaction in this or other studies indicates a potential health hazard to patients
4. Plans to modify or discontinue the development of the study drug
5. Determination of futility

In the event Bristol-Myers Squibb decides to no longer supply study drug, ample notification will be provided so that appropriate adjustments to patient treatment can be made.

6 STUDY AGENT

6.1 STUDY AGENT(S) AND CONTROL DESCRIPTION

6.1.1 ACQUISITION

Study agent will be supplied by the manufacturer, Bristol-Myers Squibb to the Moffitt Investigational Pharmacy.

6.1.2 FORMULATION, APPEARANCE, PACKAGING, AND LABELING

The dosage form labeled for clinical trials is a hard gelatin capsule Reddish brown, opaque, size 0 capsule, printed with "FEDR 100 mg" in white ink for oral administration. Each capsule contains 100 mg fedratinib (equivalent to 117.30 mg fedratinib dihydrochloride monohydrate) with the following excipients: silicified microcrystalline cellulose and sodium stearyl fumarate.

Bristol-Myers Squibb will supply fedratinib 100 mg capsules for oral administration in high density polyethylene (HDPE) bottles with heat induction seal (tamper-resistant) and polypropylene child-resistant closures, labeled appropriately as Investigational Product.

6.1.3 PRODUCT STORAGE AND STABILITY

Store as directed on the package label: fedratinib must be stored at temperatures below 86°F (30°C).

6.1.4 PREPARATION

Bristol Myers Squibb will supply fedratinib 100 mg capsules for oral administration in high density polyethylene (HDPE) bottles with heat induction seal (tamper-resistant) and polypropylene child-resistant closures, labeled appropriately as Investigational Product.

6.1.5 DOSING AND ADMINISTRATION

Fedratinib will be given at a dose of 400 mg PO once daily (4-100 mg capsules). Fedratinib can be given at any time during the day, but patients are advised to take the dose at the same approximate time every day. Patients are further advised to take their dose with a high fat meal as this may reduce the incidence of nausea and vomiting.

In patients taking concomitant strong CYP3A4 inhibitors that are deemed necessary by study PI (see section 7.6), fedratinib dose should be reduced to 200 mg once daily. In cases where co-administration with a strong CYP3A4 inhibitor is discontinued, fedratinib dose should be increased to 300 mg once daily during the first two weeks after discontinuation of the CYP3A4 inhibitor, and then to 400 mg once daily thereafter.

If a daily dose of fedratinib is missed, the next scheduled dose should be taken the following day. A dose will be considered “missed” if it is not administered within 8 hours of the typical time of administration. Missed doses do not need to be made up.

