6.1.6 DOSE ADJUSTMENTS/MODIFICATIONS/DELAYS

Patients will be treated at a starting dose of fedratinib 400 mg PO daily, unless they require co-administration with a strong CYP3A4 inhibitor, in which case, fedratinib dose will be reduced to 200 mg PO daily (see section 7.5). There will be no dose escalation above the 400 mg PO daily dose. Dose interruptions and modifications should occur according to the US Package Insert and protocol-defined guidelines and, when feasible, this decision should be after discussion with the study PI. Adverse events that have a clear alternative explanation or transient (≤ 72 hours) abnormal laboratory values without associated clinically significant signs or symptoms may be exempt from dose reduction rules. Hematologic AEs that precipitate dose interruptions should be monitored for recovery for at least every 7 days, if feasible.

Guidelines for Management of Gastrointestinal Adverse Events:

Gastrointestinal adverse events, specifically nausea, vomiting and diarrhea, are commonly associated with fedratinib treatment and require multifaceted management using dose adjustment, active treatment or prophylaxis with anti-emetics, and monitoring. GI symptoms generally start in the first treatment cycle but typically improve within 6-8 weeks on fedratinib treatment.

Management of Nausea and Vomiting

Management of nausea and vomiting during treatment with fedratinib will be done according to the following steps:

- Patients will be provided management instructions (including when to contact the study site) before the start of treatment.

- In order to mitigate for nausea and vomiting events, it is recommended to take fedratinib with food during an evening meal. It is highly recommended to use anti-nausea/vomiting treatment prophylactically according to local practice for the first 8 weeks of treatment (eg, ondansetron). If dimenhydrinate or other muscarinic receptor antagonists are used for nausea and vomiting, administer these agents in the evening to minimize drowsiness and other potential neurological AEs.
- Hold / reduce the dose of fedratinib
- Hospitalization may be indicated for Grade 3 or higher nausea or vomiting or events that persist
- For medications that are administered for prophylactic use of nausea and vomiting, if no clinically significant nausea and vomiting occurs during the first 8 weeks of fedratinib treatment, consider weaning the patient off these medications

Management of Diarrhea

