Thrombocytopenia	Grade 4 or Grade 3 with bleeding	
 • Hold until resolved to $> 50 \times 10^9/L$ or baseline, if baseline was lower than $50 \times 10^9/L$. • Restart dose at 100 mg daily below last given dose. • If grade 4 thrombocytopenia persists for > 14 days, then discontinue study drug.
Neutropenia	Grade 4	
 • Interrupt dose until ANC $> 1.0 \times 10^9/L$. Restart dose at 100 mg daily below the last given

		
dose.
 
 If grade 4 neutropenia persists for > 14 days, discontinue study drug.
--	--	--

Other Toxicities	
Any Grade 1 or Grade 2	Continue study drug treatment and treat the toxicity; monitor as clinically indicated
Any grade 3 toxicity, if clinically significant and not manageable by supportive care	
 Interrupt study drug up to 2 weeks (14 days); until toxicity resolves to ≤ Grade 1 or baseline. Resume study drug at same dose. If assessed as at least possibly related to study drug, resume at next lower dose; monitor as clinically indicated
Any recurrent Grade 3 toxicity at 100 mg daily dose (lowest dose allowed on study) that is at least possibly related to study drug	
 Discontinue study drug and follow-up per Protocol. Exceptions require approval of study PI.
Any other non-hematologic Grade 4 toxicity	
 Discontinue study drug and follow-up per protocol
New red blood cell (RBC) transfusion requirement	
 Dose reduction should be considered in patients who become newly dependent upon RBC transfusions.

Dose reductions will be made in increments of 100 mg with 100 mg daily being the lowest dose to be administered on study. Any toxicity that occurs at a dose level of 100 mg daily that would require a dose reduction will result in discontinuation of study drug unless otherwise approved by the study PI.

Dose increases can occur after a dose reduction if toxicity has remained ≤ 1 or at baseline for ≥ 28 days. Dose increases will be made in increments of 100 mg daily may only occur once per cycle. Dose levels can only be tried on three occasions.

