7.5 PROHIBITED MEDICATIONS, TREATMENTS, AND PROCEDURES

Treatment with the following drugs will not be permitted unless discussed with, and approved by, the primary investigator:

- Moderate and strong CYP3A4 Inducers (should be avoided in all cases)
 - Phenytoin
 - Rifampicin
 - Enzalutamide
 - Apalutamide
 - Carbamazepine
 - Bosentan
 - Efavirenz
 - Phenobarbital
 - Primidone
 - St. John's Wort

Treatment with the following drugs is cautioned against; however, if absolutely necessary, necessitates dose reduction.

- CYP3A4 Inhibitors
 - Diltiazem
 - Erythromycin
 - Clarithromycin
 - Ketoconazole
 - Itraconazole
 - Voriconazole
 - Posaconazole
 - Fluconazole
 - Ritonavir
 - Aprepitant
 - Ciprofloxacin

- Cyclosporine
- Dronedarone
- Fluconazole
- Imatinib
- Fluovaxamine
- Verapamil

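### Read literally, 6.1.5 returns a patient with a toxicity dose reduction to 300 mg and then 400 mg when a strong CYP3A4 inhibitor stops; the text does not say that the 6.1.6 conditions still govern

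*Combined protocol and SAP*

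**What the plan says.** Section 6.1.5 sets the dose at 400 mg once daily. If the study PI deems a strong CYP3A4 inhibitor necessary, the "fedratinib dose should be reduced to 200 mg once daily". After the inhibitor stops, fedratinib is "increased to 300 mg once daily during the first two weeks after discontinuation of the CYP3A4 inhibitor, and then to 400 mg once daily". No toxicity condition is attached and no group of patients is excepted.

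Section 6.1.6 has its own rule for going back up: "Dose increases can occur after a dose reduction if toxicity has remained ≤ 1 or at baseline for ≥ 28 days". It adds: "Dose increases will be made in increments of 100 mg daily may only occur once per cycle". Reductions are also in 100 mg steps, with 100 mg daily as the lowest dose. The section repeats the 200 mg dose for use with a strong inhibitor and sets a ceiling of 400 mg, but it is silent on what happens when the inhibitor stops. Its general direction is that "Dose interruptions and modifications should occur according to the US Package Insert and protocol-defined guidelines". The PI's part in this is qualified: "when feasible, this decision should be after discussion with the study PI".

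Section 7.5 cautions against CYP3A4 inhibitors, whose use, "if absolutely necessary, necessitates dose reduction". Section 5.2 excludes patients taking "dual CYP3A4 and CYP2C19 inhibitors" at entry.

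**The concern.** A patient can fall under both rules: reduced for a fedratinib toxicity, with that reduction still in force, and also taking a strong inhibitor that is then stopped. Section 6.1.5 names fixed doses of 300 mg and 400 mg. It does not say to return to the previous dose. Taken alone, it brings the patient back to 400 mg within 15 days whatever the toxicity history. Section 6.1.6 would first ask for 28 quiet days. No section states which rule prevails.

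What is at stake is the safety of those patients and, indirectly, their time on drug. If toxicity returns after an early increase, section 6.1.6 requires discontinuation for recurrent grade 3 or higher ALT/AST elevation. Section 5.4.1 counts each further drug-related reduction towards mandatory withdrawal at three.

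**Working it through.** The plan gives no figure to reproduce. The check compares the two rules and works out when they diverge.

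**Inputs.** From 6.1.5: 200 mg with the inhibitor, 300 mg for two weeks after it stops, then 400 mg. From 6.1.6: 28 days at grade 1 or lower (or baseline), 100 mg steps, one increase per cycle, lowest dose 100 mg. From 7.3.2: a cycle is 28 days.

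**Conventions.** Day 1 is the first day after the inhibitor stops, so the literal 6.1.5 path is 300 mg on days 1–14 and 400 mg from day 15. Let t be the days already spent at grade 1 or lower (or baseline) when the inhibitor stops. Toxicity is assumed not to return, so the count at day 15 is t + 14. Percentages compare nominal doses with the toxicity-reduced dose held before the inhibitor.

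| Dose before inhibitor | Day 1 | Day 15 | 28-day condition not met |
|---|---|---|---|
| 300 mg | 300 mg, no increase | 400 mg; 400/300 − 1 = +33% | t + 14 < 28, so t = 0–13 |
| 200 mg | 300 mg; 300/200 − 1 = +50% | 400 mg; 400/200 − 1 = +100% | Day 1: t < 28, so t = 0–27. Day 15: t + 14 < 28, so t = 0–13 |
| 100 mg | 300 mg; 300/100 − 1 = +200% | 400 mg; 400/100 − 1 = +300% | As for 200 mg |

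At t of 28 days or more the 28-day condition is met in every row.

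**Step size and frequency.** The patient at 100 mg rises by 300 − 100 = 200 mg at once, against a 100 mg limit, whatever t is. For the patient at 200 mg the two increases are 14 days apart. If day 1 is day d of a cycle, the second falls on day d + 14, which is in the same cycle when d + 14 ≤ 28, that is d = 1–14. From d = 15 they fall in different cycles.

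**Reduced on the inhibitor.** A patient first reduced for toxicity from 200 mg to 100 mg while taking the inhibitor is also sent to 300 mg when it stops, again a 200 mg step.

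**Dose while on the inhibitor.** The flat 200 mg is a reduction from 400 or 300 mg. It is no reduction for a patient already at 200 mg, and it is double the dose of a patient at 100 mg. Section 7.5 nevertheless says that inhibitor use requires a reduction.

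**The case against.** The two sections can be read together. Section 6.1.5 starts from 400 mg, and its 200/300/400 mg path reverses a reduction made for a drug interaction. Section 6.1.6 deals with toxicity and is nowhere switched off. An advisory instruction that meets a standing safety condition is ordinarily carried out once the condition is met. The study PI has already judged the inhibitor necessary and should, when feasible, discuss dose changes. The US Package Insert may also settle the case.

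Much of this stands. A reader might infer a firm contradiction, or an order to re-escalate regardless of toxicity; the documents do not support that, because 6.1.6 remains in force and reading it as governing is natural. What remains is that the text does not say so. The PI's ruling on need concerns the inhibitor, not the dose after it stops; the discussion is qualified and names no dose; and the insert is not among the documents, so it cannot be checked.

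The group is also narrow. For ALT/AST, amylase/lipase and other grade 3 toxicities, drug generally resumes after return to grade 1 or baseline. If that level holds, the whole inhibitor course counts towards t, and a short t needs a short course soon after recovery. Restart after thrombocytopenia or neutropenia depends on count thresholds instead, so that reassurance does not automatically extend to them.

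Finally, the percentages are ratios of nominal doses. The documents give no pharmacokinetic data, so they cannot be read as increases in exposure.

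**Conclusion.** The point holds as a gap in wording with a safety consequence for a small subgroup. Followed literally, 6.1.5 can take a patient back to a dose already abandoned for toxicity without the check that 6.1.6 sets. The 28-day condition is breached only at t of 0–13 days for a patient at 300 mg and 0–27 days for a patient at 200 mg. For patients at 100 mg the 100 mg step limit is also exceeded.

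This assumes that the unlabelled limit of 1 in 6.1.6 means grade 1, that the 28-day count does not restart after the first increase, and that a site applies 6.1.5 alone. The documents give no number affected. It is likely to be few of the 25, since strong inhibitors need the PI's agreement, are cautioned against, and dual CYP3A4/CYP2C19 inhibitors are excluded at entry.

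Two wider inferences are not supported. The 300/400 mg path is not in dispute for a patient never reduced for toxicity, who is simply restored to the starting dose. Nor does the point reach sample size, power, type I error or the primary analysis.

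**What to change.** Amend 6.1.5 to say:

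- The 300/400 mg path applies only to patients with no toxicity reduction in force, whether made before or during inhibitor use.
- A patient reduced for toxicity before the inhibitor resumes at no more than the last tolerated pre-inhibitor dose (300, 200 or 100 mg).
- A patient first reduced for toxicity while on the inhibitor keeps the current dose when the inhibitor stops.
- In both cases any further increase follows 6.1.6.
- The on-inhibitor dose for patients already at 200 or 100 mg is stated, so that 6.1.5 agrees with 7.5.

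The cost is a few sentences at the next amendment, with no new data, visits or patients. The downside is that some patients may stay on a lower dose for a few weeks longer.
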